1. INTRODUCTION

This statistical analysis plan (SAP) is based on the final protocol (v1.0) dated 13-May-2019. The plan covers statistical analysis, tabulations and listings of the study data to investigate the pharmacokinetics (PK) and safety.

The SAP is prepared by Mitsubishi Tanabe Pharma Corporation (MTPC). The statistical analysis and production of the outputs described in the SAP and QC will be conducted by [REDACTED]. The final analysis and outputs will be checked by [REDACTED] and approved by MTPC Data Science Department.

Any statistical analysis details described in this document supersede any description of statistical analysis in the protocol.

2. STUDY OBJECTIVE AND ENDPOINTS

2.1. Study Objectives

Primary objective: To evaluate the effect of food on the PK of oral edaravone in healthy adult subjects.

Secondary objective: To evaluate the PK, safety, and tolerability of oral edaravone.

2.2. Study Endpoints

2.2.1. Safety Assessments

- (1) Adverse events and adverse drug reactions
- (2) 12-lead ECG
- (3) Laboratory tests
- (4) Vital signs

2.2.2. Pharmacokinetics Assessments

- (1) Drug concentration (in plasma and urine)
Unchanged edaravone, sulfate conjugate, and glucuronide conjugate
- (2) Pharmacokinetic parameters
Unchanged edaravone: AUC_{0-24} , AUC_{0-t} , $AUC_{0-\infty}$, C_{max} , t_{max} , $t_{1/2}$, Kel, MRT, CL/F, V_z/F , V_{ss}/F , Ae, Ae%, CLr
Sulfate conjugate and glucuronide conjugate: AUC_{0-t} , AUC_{0-24} , $AUC_{0-\infty}$, C_{max} , t_{max} , $t_{1/2}$, Kel, Ae, Ae% (t: Final concentration measurable time point)
Other PK parameters (for all PK profiles for which the Kel has been calculated): $AUC\%_{ex}$, Adjusted R^2 , Number of Kel points, Lower limit of Kel, Upper limit of Kel

3. STUDY DESIGN

3.1. Phase and Type of the Study

Phase of the study : Phase I

Type of the study: Clinical pharmacology study

3.2. Study Design

3.2.1. Type and Details of Cohorts

Single-dose, randomization, open-label, crossover study

Group	Period I (at Day 1)	Period II (at Day 3)	Period III (at Day 5)	Period IV (at Day 7)	Period V (at Day X+1)
1	A	B	C	D	The diet condition will be determined based on the PK data collected from period I to period IV. *) (E, F, or G etc.)
2	B	C	D	A	
3	C	D	A	B	
4	D	A	B	C	

A: Dosing under fasted condition

B: Dosing 8 hours after high-fat meal

C: Dosing 4 hours after low-fat meal

[figure not shown]
D: Dosing 2 hours after light meal

*) The diet menu (any one of high-fat meal, low-fat meal and light meal) and dosing time after a meal (within a range of 30 minutes to 10 hours after a meal) in period V will be determined based on the PK data collected from period I to period IV. The possible case of the diet condition includes the following.

E: Dosing 2 hours after low-fat meal

F: Dosing 4 hours after light meal

G: Dosing 8 hours after low-fat meal

3.2.2. Study Period and Evaluation Period

Study period: The study period is defined as the period from the time of obtaining the informed consent to the time of completion of the end-of-study assessment or discontinuation assessment (for subjects who have entered into the follow-up period, to the time of completion or termination of the follow-up).

Screening: Subjects providing informed consent will be screened for eligibility to select subjects meeting all of the inclusion criteria and none of the exclusion criteria (16 subjects with a few reserve subjects).

Evaluation period: The evaluation period is defined as the period from completion of dosing of the investigational product on Day 1 to completion of the end-of-study assessment or discontinuation assessment. The duration of hospitalization will be 10 days and 9 nights

(Day -1 to Day 9) for Period I to Period IV, and 4 days and 3 nights (Day X to Day X+3) for Period V.

End-of-study assessment: The prespecified observations and tests will be performed as the end-of-study assessment, 7 days (± 2 days) after the last dose of the investigational product.

3.3. Schedule of Study Procedures

Group 1: Period I to IV

Day (time window)	Informed consent	Screening Day -30 to -2	Period I (A: Dosing under fasted condition)						Period II (B: Dosing 8 hours after high-fat meal)						
			-1	1	2	3	4	5	6	7	8	9			
Time after dosing		Visit	Admission												
			Pre-dose	0	5 m	15 m	30 m	45 m	1 h	1 h 30 m	2 h	4 h	6 h	8 h	
Written informed consent	X														
Subject characteristics	X														
Eligibility assessment	X	X	X												
Food (High* Low* Light*) ^a															
Dosing of edaravone			X												
Height/weight/BMI ^b	X	X													
Physical examination	X	X	X												
Vital signs	X	X	X												
12-lead ECG	X	X	X												
Laboratory tests	X	X													
Serological tests	X														
Drug/alcohol abuse screening	X														
Pregnancy test in female	X	X													
Adverse events ^c	<														
Concomitant medications	<														
Blood sampling for edaravone	X	X	X	X	X	X	X	X	X	X	X	X	X	X	
Urine sampling for edaravone ^d	<	<	<	<	<	<	<	<	<	<	<	<	<	<	
Time after dosing		Before meal	4 h Pre-dose	48 h	0	5 m	15 m	30 m	45 m	1 h	1 h 30 m	2 h	4 h	6 h	8 h Pre-dose
			Pre-dose												Pre-dose
															48 h
															0
															5 m
															15 m
															30 m
															45 m
															1 h
															1 h 30 m
															2 h
															4 h
															6 h
															8 h
															10 h
															12 h
															14 h
															16 h
															18 h
															20 h
															22 h
															24 h
															36 h
															48 h

At the time of withdrawal, the same tests will be performed as those of the end-of-study assessment in period V.

- High: High-fat meal. Low: Low-fat meal. Light: Light meal
- Height will be measured at screening only. Body weight will be measured at screening, admission, and end-of-study assessments. BMI will be calculated at screening and admission assessment.
- Assess serious adverse events beginning after informed consent is obtained. Survey of other adverse events will be started after administration of the investigational product is started.
- Urine volume is measured for each void. A portion of the urine is collected, dispensed into a tube containing stabilizer, and stored frozen. The urine is forced to void at 24-hour intervals.

Group 2: Period I to IV

At the time of withdrawal, the same tests will be performed as those of the end-of-study assessment in period V.

- a) High: High-fat meal, Low: Low-fat meal, Light: Light meal
- a) Height will be measured at screening only. Body weight will be measured at screening, admission, and end-of-study assessments. BMI will be calculated at screening and admission assessment.
- b) Assess serious adverse events beginning after informed consent is obtained. Survey of other adverse events will be started after administration of the investigational product is started.
- c) Urine volume is measured for each void. A portion of the urine is collected, dispensed into a tube containing stabilizer, and stored frozen. The urine is forced to void at 24-hour intervals.

Group 3: Period I to IV

Day (time window)	Informed consent	Screening Day -30 to -2	Period I (C: Dosing 4 hours after low-fat meal)										Period II (D: Dosing 2 hours after light meal)										
			-1					1					2					3					
Time after dosing		Visit																					
Written informed consent	X																						
Subject characteristics		X																					
Eligibility assessment		X	X																				
Food (High-Low-Light) ^a			Low																				
Dosing of edaravone				X																			
Height, weight, BMI ^b	X	X																					
Physical examination	X	X	X	X																			
Vital signs	X	X	X	X																			
12-lead ECG	X	X	X	X																			
Laboratory tests	X	X																					
Serological tests		X																					
Drug/alcohol abuse screening		X																					
Pregnancy test in female		X	X																				
Adverse events ^c																							
Concomitant medications																							
Blood sampling for edaravone			X	X	X	X	X	X	X	X	X	X	X	X	X	X	X	X	X	X	X	X	X
Urine sampling for edaravone ^d																							

Day (time window)	Period III (A: Dosing under fasted condition)										Period IV (B: Dosing 8 hours after high-fat meal)											
	5					6					7					8					9	
Time after dosing	Pre-dose	48 h	0	5 m	15 m	30 m	45 m	1 h	1 h 30 m	2 h	4 h	6 h	8 h	10 h	12 h	24 h	36 h	46 h	0	5 m	15 m	30 m
Written informed consent																						
Subject characteristics																						
Eligibility assessment																						
Food (High-Low-Light) ^a																						
Dosing of edaravone	X																					
Height, weight, BMI ^b																						
Physical examination	X																					
Vital signs	X																					
12-lead ECG	X																					
Laboratory tests	X																					
Serological tests																						
Drug/alcohol abuse screening																						
Pregnancy test in female																						
Adverse events ^c																						
Concomitant medications																						
Blood sampling for edaravone	X	X	X	X	X	X	X	X	X	X	X	X	X	X	X	X	X	X	X	X	X	X
Urine sampling for edaravone ^d	X																					

At the time of withdrawal, the same tests will be performed as those of the end-of-study assessment in period V.

- High: High-fat meal, Low: Low-fat meal, Light: Light meal
- Height will be measured at screening only. Body weight will be measured at screening, admission, and end-of-study assessments. BMI will be calculated at screening and admission assessment.
- Assess serious adverse events beginning after informed consent is obtained. Survey of other adverse events will be started after administration of the investigational product is started.
- Urine volume is measured for each void. A portion of the urine is collected, dispensed into a tube containing stabilizer, and stored frozen. The urine is forced to void at 24-hour intervals.

Group 4: Period I to IV

Day (time window)	Informed consent	Screening Day -30 to -2	Period II (D: Dosing 2 hours after light meal)				Period II (A: Dosing under fasted condition)			
			-1	1	2	3	4			
Time after dosing		Visit	Admission	1 h Pre-dose	Pre-dose	0	5 m	15 m	30 m	45 m
Written informed consent	X									
Subject characteristics	X									
Eligibility assessment	X	X	X							
Food (High-Low-Light) ^a			Light							
Dosing of edaravone				X						
Height, weight, BMI ^b	X	X								
Physical examination	X	X	X							
Vital signs	X	X	X							
12-lead ECG	X	X	X							
Laboratory tests	X	X								
Serological tests	X									
Drug/alcohol abuse screening	X									
Pregnancy test in female	X	X								
Adverse events ^c	←									
Concomitant medications	←									
Blood sampling for edaravone			X	X	X	X	X	X	X	X
Urine sampling for edaravone ^d	←		↑	X	X	X	X	X	X	X

Day (time window)	Period III (B: Dosing 3 hours after high-fat meal)				Period IV (C: Dosing 4 hours after low-fat meal)			
	5	6	7	8	9			
Time after dosing	8 h Pre-dose	Pre-dose	48 h	0	5 m	15 m	30 m	45 m
					1 h	1 h 30 m	2 h	4 h
					6 h		10 h	12 h
					8 h		12 h	24 h
					36 h		36 h	36 h
Written informed consent								
Subject characteristics								
Eligibility assessment								
Food (High-Low-Light) ^a	High				Low			
Dosing of edaravone		X				X		
Height, weight, BMI ^b								
Physical examination	X				X			
Vital signs	X				X			
12-lead ECG	X				X			
Laboratory tests	X							
Serological tests								
Drug/alcohol abuse screening								
Pregnancy test in female								
Adverse events ^c	←							
Concomitant medications	←							
Blood sampling for edaravone		X	X	X	X	X	X	X
Urine sampling for edaravone ^d	←	X	X	X	X	X	X	X

At the time of withdrawal, the same tests will be performed as those of the end-of-study assessment in period V.

- High: High-fat meal, Low: Low-fat meal, Light: Light meal
- Height will be measured at screening only. Body weight will be measured at screening, admission, and end-of-study assessments. BMI will be calculated at screening and admission assessment.
- Assess serious adverse events beginning after informed consent is obtained. Survey of other adverse events will be started after administration of the investigational product is started.
- Urine volume is measured for each void. A portion of the urine is collected, dispensed into a tube containing stabilizer, and stored frozen. The urine is forced to void at 24-hour intervals.

All groups: Period V

Day (time window)	Period V														End-of-study assessment ^{a)}			
	X	0	5 m	15 m	30 m	45 m	1 h	1 h 30 m	2 h	4 h	6 h	8 h	10 h	12 h	X+2	X+3	X+8 (±2)	
Time after dosing	Admission b)** h Pre-dose	Pre-dose	0	5 m	15 m	30 m	45 m	1 h	1 h 30 m	2 h	4 h	6 h	8 h	10 h	12 h	24 h	36 h	Discharge/48 h ^{b)}
Food ^{a)}	X																	
Dosing of edaravone		X																
Weight	X																X	
Physical examination	X	X					X										X	
Vital signs	X	X					X										X	
12-lead ECG	X	X					X										X	
Laboratory tests	X																X	
Pregnancy test in female																	X	
Adverse events ^{c)}	←													→				
Concomitant medications	←													→				
Blood sampling for edaravone		X	X	X	X	X	X	X	X	X	X	X	X	X	X	X		
Urine sampling for edaravone ^{d)}		←												→				

- a) The diet menu in period V will be determined based on the PK data collected from period I to IV.
- b) The dosing time after a meal in period V will be determined based on the PK data collected from period I to IV.
- c) Assess serious adverse events beginning after informed consent is obtained. Survey of other adverse events will be started after administration of the investigational product is started.
- d) Urine volume is measured for each void. A portion of the urine is collected, dispensed into a tube containing stabilizer, and stored frozen. The urine is forced to void at 24-hour intervals.
- e) At the time of withdrawal, the same tests will be performed as those of the end-of-study assessment.
- f) In the F: Dosing 4 hours after light meal, tests/observations are conducted 46 hours after administration of the investigational product.

3.4. Sample Size and Power Considerations

Total of 16 subjects (4 subjects per group)

[Rationales for setting]

The target number of subjects was set on the assumption that it would allow obtaining results that will meet the study objectives although it is not based on statistical calculations.

4. PLANNED ANALYSIS

4.1. Final Analysis

This SAP will be finalized before database lock. Final data analysis will be conducted after database lock.

5. ANALYSIS POPULATIONS

PK analysis will be performed on the PK analysis set. Safety analysis will be performed on the safety analysis set (SAF). The definitions of the analysis sets are provided below. The detailed handling of subjects was determined by the sponsor, by the time of the data lock.

(1) PK analysis set

The PK analysis set will consist of all subjects who received at least 1 dose of the investigational product and had evaluable PK data.

(2) Safety analysis set

The SAF will consist of all subjects who received at least 1 dose of the investigational product.

6. STATISTICAL CONSIDERATIONS

6.1. Descriptive Statistics

(1) Non-PK related

Continuous data will be summarized descriptively using the number in the analysis set (N), the number of observations (n), mean, standard deviation (SD), median, minimum and maximum. Categorical data will be summarized using frequency counts and percentages. The denominator for the percentages will be the total number of subjects in the treatment group and analysis population being presented, unless otherwise specified.

(2) PK related

Plasma concentrations will be summarized descriptively using N, n, mean, SD, median, minimum and maximum.

The plasma and urine PK parameters will be summarized descriptively using N, n, arithmetic mean, SD, median, CV%, range (minimum, maximum), geometric mean and geometric CV%. CV% and Geometric CV% will be calculated as follows:

$$CV\% = \frac{\text{standard deviation}}{\text{arithmetic mean}} \times 100$$

$$\text{Geometric CV\%} = \sqrt{[\exp(\sigma^2) - 1]} \times 100$$

where σ represents the standard deviation computed on the natural logarithmic transformed concentrations.

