Systolic and diastolic blood pressure will be measured after at least a 5-minute rest in a lying position. One measurement will be taken for each time point. The measurements will be taken in the same arm throughout the study period, in principle.

If the timing of measurement is the same as that of blood sampling, it should be conducted before blood sampling.

Confidential

Time points

Screening	No specifications ^{b)}
Day -1 (hospitalization)	No specifications ^{b)}
Day 1	Pre-dose, and 1 hour post-dose
Day 2	24 hours post-dose
Day 3	Pre-dose, and 1 hour post-dose
Day 4	24 hours post-dose
Day 5	Pre-dose, and 1 hour post-dose
Day 6	24 hours post-dose
Day 7	Pre-dose, and 1 hour post-dose
Day 8	24 hours post-dose ^{b)}
Day 9 (discharge)	48 hours post-dose ^{b), c)}
Day X ^{a)} (hospitalization)	No specifications ^{b)}
Day X+1 ^{a)}	Pre-dose, and 1 hour post-dose
Day X+2 ^{a)}	24 hours post-dose ^{b)}
Day X+3 ^{a)} (discharge)	48 hours post-dose ^{b), c)}
End-of-study assessment or withdrawal assessment	No specifications ^{b)}

a) X = Day of hospital admission in period V

b) To be performed in the fasting state (before breakfast).

c) In the C: Dosing 4 hours after low-fat meal and F: Dosing 4 hours after light meal, the measurement is conducted 46 hours post-dose.

(3) 12-lead ECG

After at least a 5-minute rest in a lying position, a 12-lead ECG will be recorded at the time points shown in the table below. The investigator (or subinvestigator) will record the date and time of measurement, heart rate, QTcF interval, PR interval, QT interval, RR interval, QRS interval, and findings in the CRF.

If the timing of measurement is the same as that of blood sampling, it should be conducted before blood sampling.

Time points

Screening	No specifications ^{b)}
Day -1 (hospitalization)	No specifications ^{b)}
Day 1	Pre-dose, and 1 hour post-dose
Day 2	24 hours post-dose
Day 3	Pre-dose, and 1 hour post-dose
Day 4	24 hours post-dose
Day 5	Pre-dose, and 1 hour post-dose
Day 6	24 hours post-dose
Day 7	Pre-dose, and 1 hour post-dose
Day 8	24 hours post-dose ^{b)}
Day 9 (discharge)	48 hours post-dose ^{b), c)}
Day X ^{a)} (hospitalization)	No specifications ^{b)}
Day X+1 ^{a)}	Pre-dose, and 1 hour post-dose
Day X+2 ^{a)}	24 hours post-dose ^{b)}
Day X+3 ^{a)} (discharge)	48 hours post-dose ^{b), c)}
End-of-study assessment or withdrawal assessment	No specifications ^{b)}

a) X = Day of hospital admission in period V

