b) To be performed in the fasting state (before breakfast).

Confidential

c) In the C: Dosing 4 hours after low-fat meal and F: Dosing 4 hours after light meal, the test is conducted 46 hours post-dose.

(4) Physical examination

At the times shown in the table below, the investigator (or subinvestigator) will examine the subject and record the examination date and findings in the CRF.

Time points

Screening	No specifications
Day -1 (hospitalization)	No specifications
Day 1	Pre-dose, and 1 hour post-dose
Day 2	24 hours post-dose
Day 3	Pre-dose, and 1 hour post-dose
Day 4	24 hours post-dose
Day 5	Pre-dose, and 1 hour post-dose
Day 6	24 hours post-dose
Day 7	Pre-dose, and 1 hour post-dose
Day 8	24 hours post-dose
Day 9 (discharge)	48 hours post-dose ^{b)}
Day X ^{a)} (hospitalization)	No specifications
Day X+1 ^{a)}	Pre-dose, and 1 hour post-dose
Day X+2 ^{a)}	24 hours post-dose
Day X+3 ^{a)} (discharge)	48 hours post-dose ^{b)}
End-of-study assessment or withdrawal assessment	No specifications

a) X = Day of hospital admission in period V

b) In the C: Dosing 4 hours after low-fat meal and F: Dosing 4 hours after light meal, the test is conducted 46 hours post-dose.

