6.3. Data Review Meeting

Prior to database lock, a data review meeting (DRM) was conducted at November 26, 2019. Protocol deviation and handing of subjects and records, for analysis sets and evaluations, was confirmed during DRM.

No protocol deviation was observed during the study. As a results of DRM, all subject was included in SAF and PK analysis set.

The PK data handling was assessed during DRM. All PK data were considered valid and included in the calculation of PK parameters and in the summary tables and figures.

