7.2. Analysis Visit Definitions

(1) Non-PK related

The date of the first dose of investigational product is defined as Day 1.

Excepted for laboratory, baseline will be the last observed value of the parameter of interest prior to the first intake of investigational product by each treatment period (this includes unscheduled visits). For laboratory, baseline will be the last observed value of the parameter of interest prior to the first intake of investigational product (this includes unscheduled visits).

No analysis visit window will not be perfomed for safety evaluation.

(2) PK related

The allowable time window will be the following.

Plasma PK sampling

Nominal Time Point	Window
Predose	Within 60 min before dosing
0.083 h after dosing	Nominal time point \pm 1 min
0.25, 0.5, 0.75, 1, 1.5, 2, 4, 6, 8, 10, 12 h after dosing	Nominal time point \pm 5 min
24, 36 h after dosing	Nominal time point \pm 15 min
48 h* after dosing *Following the dosing 4 hours after meals, blood sampling is conducted 46 h after dosing	
Blood sampling 46 h after dosing	[Period I, II, and III] 45~47 h after dosing and within 60 min before the dosing in the next period [Period IV and V] 45~47 h after dosing
Blood sampling 48 h after dosing	[Period I, II, and III] 47~50 h after dosing and within 60 min before the dosing in the next period [Period IV and V] 47~50 h after dosing

Urine PK sampling

Nominal Time Point	Window
Predose	Within 60 min before dosing
Voluntary Urine	—
Forced micturition at 24 h after dosing	Nominal time point \pm 30 min

Nominal Time Point	Window
Forced micturition at 48* hours post-dose * Forced micturition at 46 h post-dose for subjects dosed 4 h after meals	
Forced micturition at 46 h after dosing	[Periods I, II, and III] 45~47 h after dosing and within 60 min before the dosing in the next period [Periods IV, V] 45~47 h post-dose
Forced micturition at 48 h after dosing	[Periods I, II, and III] 47~50 h after dosing and within 60 min before the dosing in the next period [Periods IV, V] 47~50 h post-dose

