7.3. Data Handling Convention for Missing Data

(1) Non-PK related

Adverse events:

If severity or relationship is found to be missing the most severe occurrence will be imputed for the summary of interest.

Other safety:

For safety summaries, only observed data will be used. Unless otherwise specified, missing safety data will not be imputed.

(2) PK related

For PK summaries, only observed data will be used. Missing PK data will not be imputed. When calculating Ae and Ae%, missing PK data will be imputed to 0.

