8.3.3. Vital Signs

Absolute values and changes from baseline will be summarized for the following parameters by treatment and scheduled time point.

- Systolic Blood Pressure (mmHg)
- Diastolic Blood Pressure (mmHg)
- Pulse Rate (bpm)
- Body Temperature(°C)

All data will be listed.

8.3.4. 12-Lead ECGs

Absolute values and changes from baseline will be summarized for the following parameters by treatment and scheduled time point.

- Heart Rate (beats/min)
- PR (msec)
- RR (msec)
- QRS (msec)
- QT (msec)
- QTcF (msec)

The percentage of subjects with 12-lead ECG values outside pre-defined limit will be summarized by treatment and scheduled time point.

All data (including overall evaluation) will be listed.

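### At the Day 9 ECG the SAP's default denominator divides results from 4 subjects by all 16, so non-zero QTcF limit percentages for conditions A–D come out at about a quarter of the observed rate

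*SAP*

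**What the plan says.** - **Denominator.** SAP 6.1, for non-PK data: "The denominator for the percentages will be the total number of subjects in the treatment group and analysis population being presented, unless otherwise specified".
- **ECG limits.** SAP 8.3.4: "The percentage of subjects with 12-lead ECG values outside pre-defined limit will be summarized by treatment and scheduled time point". It gives no denominator of its own. The treatments are the meal conditions listed in SAP 9.2.
- **Categories.** SAP 7.1.2.3 defines four QTcF bands that do not overlap and cover every value (above 500, 480–500, 450–480, and 450 msec or below). It adds two change-from-baseline limits, above 30 and above 60 msec.
- **Numbers.** SAP 3.4: "Total of 16 subjects (4 subjects per group".
- **Baseline.** For ECG, SAP 7.2 says "baseline will be the last observed value of the parameter of interest prior to the first intake of investigational product by each treatment period". SAP 9.3 accordingly marks the pre-dose ECGs on Days 1, 3, 5 and 7 as baselines.
- **Late ECG.** In Periods I–IV, both the ECG table in protocol 9.2.5.1 and SAP 9.3 schedule a 46/48-hour ECG only on Day 9. On its timing, the protocol notes: "In the C: Dosing 4 hours after low-fat meal and F: Dosing 4 hours after light meal, the test is conducted 46 hours post-dose". SAP 9.3 labels the whole Day 9 row as 46 hours.

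**The concern.** A percentage by condition and time point should describe the subjects who were measured there. The SAP's default divides by everyone who received the condition. In this crossover the two numbers agree where all four periods contribute an ECG, and they part where only one period does.

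The late ECG after Periods I–III does not exist as a separate assessment, because the ECG two days after each dose is used as the next condition's baseline. On Day 9, therefore, 12 of the 16 subjects in each of A–D were never scheduled for a late ECG under that condition, yet they stay in the denominator. The Period V condition is given to all groups at once and has no such gap. One table would then carry percentages on two different footings, and an entirely normal Day 9 result would print as 25% in the normal band with nothing else filled in.

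**Working it through.** **Inputs.** Sequences ABCD, BCDA, CDAB and DABC for Groups 1–4 (SAP 3.2.1); 4 subjects per group (SAP 3.4); ECG rows from SAP 9.3 and protocol 9.2.5.1; denominator rule from SAP 6.1.

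**Planned number.** 4 groups × 4 subjects = 16, as the SAP states. Every group receives each of A–D once, so N = 16 per condition if all are dosed.

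**Who receives what in Period IV.** Group 1 receives D, Group 2 A, Group 3 B and Group 4 C. That is one group of 4 per condition.

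**Subjects with an ECG, by time after dose:**

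| Condition | Pre-dose | 1 h | 24 h | 46/48 h |
|---|---|---|---|---|
| A, B, C, D (each) | 16 | 16 | 16 | 4 |
| Period V condition | 16 | 16 | 16 | 16 |

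**Percentages at Day 9 for a condition A–D,** with k subjects in a category. The rule gives k/16; the observed rate is k/4.

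| k | SAP 6.1 rule | Observed rate |
|---|---|---|
| 0 | 0 | 0 |
| 1 | 6.25% (prints 6.3%) | 25.0% |
| 2 | 12.5% | 50.0% |
| 3 | 18.75% | 75.0% |
| 4 | 25.0% | 100% |

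For every non-zero k the ratio is (k/4)/(k/16) = 16/4 = 4. The four exhaustive QTcF bands together hold all 4 measured subjects, so they sum to 4/16 = 25%. In Period V they sum to 16/16 = 100%.

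**Sensitivity.** The documents do not state the number dosed. With 14 to 16 subjects in the condition and 3 or 4 measured, the factor runs from 14/4 = 3.5 to 16/3 = 5.3.

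**Alternative layout.** SAP 9.3 keys its rows to study day plus time. If the table uses those rows, each A–D cell holds one group throughout. Condition A, for example, is Group 1 on Day 1, Group 4 on Day 3, Group 3 on Day 5 and Group 2 on Day 7. The 4/16 dilution then applies to every A–D cell from Day 1 to Day 9.

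**Day 9 label.** Of the two conditions the protocol places at 46 hours, only C occurs in Period IV, in Group 4. The other three groups, 12 of 16 subjects, are at 48 hours.

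**The case against.** **SAP 7.3 may already settle it.** It says "For safety summaries, only observed data will be used", and SAP 6.1 allows exceptions, so a programmer might use the number observed. That is possible, but SAP 7.3 sits under missing-data handling and is about not imputing. It names no denominator, and these ECGs are unscheduled rather than missing. The stated rule remains SAP 6.1.

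**Treatment group could mean the sequence group of 4.** The problem would then vanish. But the SAP keeps the two apart: laboratory results are by group (SAP 8.3.2), ECGs by treatment (SAP 8.3.4).

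**The harm is small and visible.** This largely stands. Counts are printed beside percentages. Continuous QTcF summaries for the same cells carry N and n, and all ECG data are listed. Subjects with QTcF of 450 msec or more are excluded at entry (protocol 3.3). In the earlier phase I study the suspension peaked at 0.4–0.8 hours fasted, with a terminal half-life of 5.1–11.8 hours (protocol section 1), so 46–48 hours is the least informative ECG after dosing. No test or decision rule uses these percentages.

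**Tempting stronger readings.** A reader might infer that every Day 9 percentage is wrong. A zero count stays zero and is left blank under SAP 9.1. A reader might also infer that the 1-hour and 24-hour rows are certainly safe; that holds only if rows are time after dose, which the SAP does not say. Finally, a reader might infer that the trial's cardiac safety reporting is compromised, or that the Period V condition will look four times worse. The documents do not support this: the table is one of several ECG displays, and the contrast arises only if there are late exceedances and the printed counts are ignored.

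**Conclusion.** The point holds as a defect in one descriptive table. SAP 6.1 states a denominator, SAP 8.3.4 does not override it, and at the Day 9 time point it gives non-zero ECG limit percentages for A–D that are about a quarter of the observed rate. The exhaustive QTcF bands sum to 25% there, against 100% for the Period V condition.

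The exact factor of four assumes 16 subjects dosed and 4 measured per condition. SAP 6.3 reports that "As a results of DRM, all subject was included in SAF and PK analysis set", which is consistent with this but gives no number. How far the dilution extends depends on the layout: Day 9 only if rows are time after dose, all A–D cells from Day 1 to Day 9 if rows are study days.

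Counts, continuous summaries and listings remain correct, and the primary PK objective is unaffected. The correction is worth making because it is cheap and the printed percentages would otherwise not be comparable across conditions. The Day 9 label is a separate inconsistency and does not bear on the denominator.

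**What to change.** - **SAP 8.3.4:** state that the denominator for ECG limit percentages is the number of subjects with a non-missing ECG for that condition and time point, and for the change-from-baseline limits also a baseline. Display that n. State whether rows are time after dose or study day.
- **SAP 9.3:** reconcile the Day 9 label of 46 hours with the timing notes in protocol 9.2.5.1, under which on Day 9 only condition C (Group 4) is at 46 hours and the other three groups are at 48 hours.

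The cost is two lines of SAP text and one programming change, with no new data. The small downside is that the Day 9 rows will visibly rest on n = 4 per condition, too few for a useful comparison with the 16 in Period V. Showing n makes that plain.
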